## 5. Endpoints

### 5.1. Primary Efficacy Endpoint

The primary efficacy endpoint is the proportion of subjects achieving  $\geq 75\%$  reduction from baseline in the PASI score (PASI-75) at Week 16.

### 5.2. Secondary Efficacy Endpoints

- The percent change from baseline in PASI score at all visits from Week 1 to Week 16
- The proportion of subjects achieving PASI-50, PASI-75, PASI-90, PASI-100 at all visits from Week 1 to Week 16
- Time to PASI-50 and PASI-75
- The proportion of subjects achieving a Static Physicians Global Assessment (sPGA) score of “0” (“clear”) or “1” (“almost clear”) combined with 2-point reduction on the 5-point sPGA scale at all visits from Week 1 to Week 16
- The change from baseline in affected body surface area (BSA) at all visits from Week 1 to Week 16
- The change from baseline in the itch numerical rating scale (NRS) at all visits from Week 1 to Week 16
- The change from baseline in the Dermatology Life Quality Index (DLQI) score at all visits from Week 1 to Week 16
- Percentage of subjects with at least a 5-point reduction from baseline in the DLQI score at all visits from Week 1 to Week 16

### 5.3. Exploratory Endpoints

CCI

This document is confidential.

#### **5.4. Pharmacokinetic Endpoints**

The PK endpoint is the trough plasma concentration ( $C_{trough}$ ) of ME3183 and its metabolite (CCI [REDACTED]).

CCI [REDACTED]

#### **5.6. Safety Endpoints**

The safety endpoints are as follows:

- The incidence, severity, and seriousness of AEs reported over the 16-week Treatment Period and the 4-week Follow-up Period
- Changes from baseline in CS physical examination findings and vital sign measurements (blood pressure, heart rate, respiratory rate, body temperature, and body weight) over the 16-week Treatment Period and the 4-week Follow-up Period
- Changes from baseline in ECG findings over the 16-week Treatment Period and the 4-week Follow-up Period
- Changes from baseline in safety laboratory values (hematology, coagulation, blood chemistry, and urinalysis) over the 16-week Treatment Period and the 4-week Follow-up Period

This document is confidential.

## 6. Analysis Sets

### 6.1. Screened Set

All subjects who have signed ICFs will be included in the screened set.

### 6.2. Randomized Set

All subjects who have signed ICFs and have received a randomization number within the IWRS will be included in the randomized set.

### 6.3. Safety Analysis Set

All randomized subjects who received at least 1 dose of study drug will be included in the safety analysis set. Analyses in the safety analysis set will be based on the study treatment actually received by each subject.

In the event of drug mis-dispensation, the following guidelines will be followed:

- For subjects randomized to the placebo group but received any active study drug, they will be included in the active treatment group corresponding to the largest number of kits dispensed.
- For subjects randomized to any one of the four active treatment groups, they will be included in the active treatment corresponding to the largest number of kits dispensed.

The Safety Analysis Set will be used for all analyses of safety endpoints.

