## 9.7. Extent of Exposure

Treatment duration will be summarized by treatment and overall using the Safety Analysis Set.

Subject data listings of study drug dispensation records will be provided.

Treatment duration (in days) is calculated as the date of the last dose of study drug – the date of the first dose of study drug + 1.

The specific definitions of the first dose and last dose dates of study drug are given below:

- First dose date: The date of the first dose of study drug that is dispensed at Week 0/Visit 2 obtained from the study drug exposure eCRF page.
- Last dose date: The date of the last dose of study drug obtained from the end of treatment eCRF page for subjects who have completed the treatment or discontinued early.

Summary statistics for treatment duration (in days), as well as a frequency summary of treatment duration categories (<7 days, 7 - <14 days, 14 - <28 days, 28 - <56 days, 56 - <84 days, 84 – ≤112 days, > 112 days), will be provided.

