### 13.1. Adverse Events

An AE is any symptom, physical sign, syndrome, or disease that either emerges during the study or, if present at Screening, worsens during the study, regardless of the suspected cause of the event. AEs will be collected from the time the subject signs the ICF through 4 weeks after the last dose of study drug.

AEs will be coded according to the MedDRA Version 24.1 or higher. Unless otherwise specified, AEs will be summarized by SOC and PT by treatment group and overall, with SOCs presented in the standard international order and PTs within SOCs presented in descending order of subject incidence.

Adverse events are summarized by subject incidence rates. In any tabulation, a subject contributes only once to the count for a given SOC or PT. If a subject experiences more than 1 occurrence of the same AE, the occurrence with the greatest severity and the closest association with the study drug will be used in the summary tables.

For the purposes of this study, any AEs classified as 'Unrelated' or 'Unlikely' will be considered as 'Not Related' and 'Possibly', 'Probably', or 'Definitely' as 'Related' to the study treatment. Missing relationship will be considered related to study product.

All AEs will be listed by subject, along with information regarding onset, duration, relationship and severity to study drug, seriousness, action taken with study drug, and outcome.

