#### 13.1.1. Treatment-Emergent Adverse Events

A Treatment-Emergent Adverse Event (TEAE) is an AE that occurred during the study after the first dose of study drug or that was present prior to dosing and exacerbates after the first dose of study drug.

If the treatment-emergent status of an AE is unclear due to a missing/incomplete start date, it will be considered treatment-emergent. Date imputation rules for missing AE start dates are described in [Section 8.3](#).

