### 13.1.4. TEAEs by Time of Onset

All TEAEs will be summarized by time of onset (Day 1 – 3, Day 4 – 7, Day 8 – 14, Day 15 – 21, Day 22 – 28, Day 29 – 56, Day 57 – 84, Day 85 – 113, Day 114+), where an overall summary of the numbers and percentages of subjects with any TEAEs within a particular time of onset period will be calculated along with further breakdown by SOC and PT.

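### The SAP's mis-dispensation rule gives each affected subject a single active group, so events that began on placebo or on another dose are tabulated there, and a placebo-only subject randomised to active has no group

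*SAP*

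**What the plan says.** SAP 6.3 opens with the as-treated principle: "Analyses in the safety analysis set will be based on the study treatment actually received by each subject". Two guidelines for mis-dispensation follow.

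- Randomised to placebo: "For subjects randomized to the placebo group but received any active study drug, they will be included in the active treatment group" for which the most kits were dispensed.
- Randomised to any of the four active groups: "they will be included in the active treatment corresponding to the largest number of kits dispensed".

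The section then extends this single label to every safety output: "The Safety Analysis Set will be used for all analyses of safety endpoints". Protocol 15.2 has the as-treated principle only, with no kit-count rule.

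Four other parts of the SAP bear on the point.

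- Under 13.1.1 a TEAE "is an AE that occurred during the study after the first dose of study drug". Study drug here includes placebo.
- Under 13.1.4, "All TEAEs will be summarized by time of onset", in bands of study day and not by the product in use.
- Under 13.1, "All AEs will be listed by subject, along with information regarding onset, duration, relationship and severity to study drug". The product taken at onset is not among the listed items.
- Under 9.7, "Subject data listings of study drug dispensation records will be provided". Treatment duration is the span from first to last dose of study drug, not divided by product.

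For the PK set (6.6), a mis-dispensed subject who received more than one active drug is excluded, not assigned to one dose.

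**The concern.** A subject-level label cannot describe a subject who took two products at different times. Three consequences follow from the wording.

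1. A subject randomised to placebo who receives one active kit late in the trial moves to an active group with all of his or her history. Events that started before any ME3183 was dispensed become TEAEs of that dose.
2. A subject who received two active doses is placed under the one with more kits. Events that started during the shorter period on the other dose are charged to the wrong dose.
3. A subject randomised to active but dispensed only placebo is sent to an active treatment by kit count, and there is no active kit to count.

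Safety and tolerability is a secondary objective, and Protocol 5.4 says the results will inform the dosing regimens of the next study. With 25 subjects planned per group, a single subject is visible in the incidence tables.

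**Working it through.** The documents give no figure on this point and no formal sample size calculation, so there is nothing to reproduce. The check has three parts.

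**1. Does anything downstream correct the label?** Take a subject randomised to placebo, with an event on Day 3 and a first active kit at Visit 7 (Day 85).

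- 13.1.1: the event follows the first dose of study drug (placebo), so it is a TEAE.
- 6.3: the subject belongs to an active group in all safety tables.
- 13.1.4: the event falls in the Day 1–3 band of that active group, although ME3183 was first dispensed 82 days later (85 − 3).
- No section divides events or exposure by product, or plans an analysis without such subjects.

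So the label is not corrected in any table. The listings allow a manual cross-check only.

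**2. How much treatment time can be misplaced?** Inputs: dispensing at Days 1, 8, 15, 29, 57 and 85 (Table 1), and dosing from Day 1 to Day 112. If a placebo subject's first active kit comes at a given visit, the placebo time before it is (day − 1)/112.

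| First active kit | Placebo days before | Share of 112 |
|---|---|---|
| Day 8 | 7 | 6.25% |
| Day 15 | 14 | 12.5% |
| Day 29 | 28 | 25% |
| Day 57 | 56 | 50% |
| Day 85 | 84 | 75% |

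If active drug is taken in one dispensing interval only (7, 14 or 28 days), total placebo time is 1 − 7/112 = 93.75%, 1 − 14/112 = 87.5% or 1 − 28/112 = 75%. Some of that may follow the active interval, where carry-over is possible. Only the time in the table is certainly free of ME3183.

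Between two active doses, assume 16 kits of equal duration. A 9:7 split puts 7/16 = 44% of exposure under the other dose.

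**3. What does one subject do to a comparison?** Inputs: 25 per group (SAP 4.3). The event counts are assumptions, because the documents give none.

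- 3/25 v 3/25 (difference 0). Move one placebo subject whose event began on placebo: 4/26 − 2/24 = 15.4% − 8.3% = 7.1 points.
- 5/25 v 3/25 (difference 8.0 points). Move one placebo subject with such an event: 6/26 − 2/24 = 23.1% − 8.3% = 14.7 points.
- The same start, but move one placebo subject without an event: 5/26 − 3/24 = 19.2% − 12.5% = 6.7 points.
- A rare event: 0/25 becomes 1/26 = 3.8% for a dose at which it did not arise.

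The contrast can rise or fall, depending on whether the moved subject had an event.

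**The case against.** The best defence is that one group per subject, with any active exposure counted as active, is a coherent as-treated convention. It keeps drug-exposed subjects out of the placebo reference, and a subject who took ME3183 did receive it. That stands for the main tables, although the SAP does not state this rationale. A reader might infer that the guidelines breach the as-treated principle and must be replaced. For subjects with mixed exposure the documents do not support that: the principle does not say how to classify someone who received two products.

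A second tempting inference is that IWRS kit numbers reveal the treatment in use when each event began. They do not. SAP 6.8 has a deviation category for a wrong kit handed to a subject, and then the IWRS assignment is not what was taken. Several packs may also be dispensed at once. A pack holds 2 × 21 = 42 capsules (Protocol 9.1.3). If each dose is 3 capsules (the one unredacted count, in Protocol 7.1), a pack lasts 42/6 = 7 days and a 28-day interval needs 4 packs. Treating a pack as a kit is an assumption. If one pack of the four is wrong, dispensing records do not date its use, and Protocol 9.5 does not say that the diary records kit numbers.

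Third, onset-based attribution needs its own rules. Protocol 5.2.2 gives a half-life of about 16 to 24 hours, so an effect can carry into a later placebo interval. AEs are also collected for 4 weeks after the last dose, when nothing is dispensed. These objections stand, and they are why the fix is supplementary.

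Finally, safety summaries are descriptive, and dispensation records, AEs and deviations are all listed, so affected subjects can be reviewed one by one. That is true, but such review leaves the tabulated counts as they are.

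**Conclusion.** The point holds in a limited form. Under SAP 6.3, events that began before any ME3183 was dispensed are tabulated as active-dose TEAEs, events in a two-dose subject all go to one dose, and the placebo-only case has no valid group. In the last case the section's opening sentence points to placebo, so one line settles it.

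The size is unknown because the number of mis-dispensed subjects is not stated. In the illustrations above, which rest on assumed event counts, moving one subject changes a between-group difference by +7.1 points (0 to 7.1), +6.7 points (8.0 to 14.7) or −1.3 points (8.0 to 6.7). If no kit was mis-dispensed, nothing changes. FAS efficacy follows the randomised group and is untouched.

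Three stronger readings go beyond the documents. The revision history shows that v1.1 added these clarifications, but not that mis-dispensation happened. No net direction of bias can be claimed, since both directions occur. Nor can the onset table be called the worst affected: all safety tables share the label, and it is only where the misplacement is easiest to see.

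**What to change.** Keep one group per subject in the main safety tables, and make these changes in SAP 6.3 and 13.1.

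- State that a subject who received only placebo kits is analysed under placebo, whatever the randomised group.
- Add supplementary versions of Tables 14.3.1.1, 14.3.1.2 and 14.3.1.8. For mis-dispensed subjects, assign each TEAE to the product dispensed for the interval in which it began, using dispensation and return records and not IWRS assignment alone.
- In these versions, count no event under an active group if it began before the first active kit, and show exposure by product.
- Fix in advance a carry-over window after the last active dose. Assign follow-up events to the last product taken, subject to that window.
- Show intervals in which more than one product was dispensed separately, as mixed.

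The cost is SAP wording and programming for the affected subjects, from records already collected. Correctly dispensed subjects are unaffected. The downside is that an affected subject can appear in two denominators of the supplementary tables, which needs a footnote. Laboratory, vital-sign and ECG summaries would keep the single-group label.

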### 6.4. Full Analysis Set

All subjects who have been randomized, received at least 1 dose of study drug, and have at least 1 evaluable post-baseline time point for primary endpoint will be included in the full analysis set (FAS). Analyses in the FAS will be based on the subject's randomized treatment group.

The FAS will be used for all analyses of efficacy endpoints.

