	
Follow-up Period assessments will be performed on Day 141.
 
After the Screening Period, approximately 125 eligible subjects with a confirmed diagnosis of psoriatic plaques, a BSA involvement of $\geq 10\%$ (at Screening and Baseline), a PASI score 12 to 40 (at Screening and Baseline), and an sPGA ≥ 3 (at Screening and Baseline) will be randomly assigned to receive ME3183 [] mg twice daily [BID], [] mg once daily [QD], [] mg BID, or [] mg QD) or placebo in a 1:1:1:1 ratio. To promote balanced allocation, randomization will be stratified by the subject's receipt (yes/no) of previous treatment with a biologic drug for psoriasis. Bio-naïve subjects will be randomized above 50% of the planned total subject randomization.
 
After randomization (Day 1), all subjects will be evaluated at Baseline and at Weeks 1, 2, 4, 8, 12, 16, and 20. Efficacy assessments (ie, PASI, BSA, sPGA, and PRO assessments [DLQI and the itch NRS]), will be assessed at Baseline (Day 1) and at Weeks 1, 2, 4, 8, 12, 16, and 20. Blood samples for PK assessment will be collected predose at Weeks 1, 4, 8 and 16. Blood samples for [] assessments will be collected predose at Baseline (Day 1), Weeks 4 and 16. Safety and tolerability will be assessed by physical exam, monitoring for AEs and serious AE (SAEs), demographics, medical history, vital signs and safety laboratory tests (hematology, coagulation, blood chemistry, and urinalysis) at Baseline (Day 1) and Weeks 1, 2, 4, 8, 12, 16, and 20. ECGs will be assessed at Baseline (Day 1) and Weeks 4, 8, 12, 16, and 20.

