7.4 Early Termination

If a subject withdraws or is terminated from study treatment prior to completion of all study periods, all data collected at Visit 8 (Day 113) should be collected at the time of early termination. The subject will be asked to return to the study site 4 weeks after the last dose of study drug to complete the follow-up visit assessments (those performed on Day 141) as indicated in the Schedule of Assessments ([Table 1](#)).

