15.2 Analysis Sets

Full Analysis Set

All subjects who have been randomized, received at least 1 dose of study drug, and have at least 1 evaluable post-Baseline time point for primary endpoint will be included in the full analysis set (FAS). Analyses in the FAS will be based on the subject's randomized treatment group.

Per Protocol Set

The per protocol set (PPS) is a subset of the FAS; the PPS will exclude subjects with protocol deviations that may significantly impact the assessment of the primary objective of the study. Analyses in the PPS will be based on the study treatment actually received by each subject. All decisions to exclude subjects from the PPS will be made prior to the unblinding of the study.

Safety Analysis Set

All randomized subjects who received at least 1 dose of study drug will be included in the safety analysis set. Analyses in the safety analysis set will be based on the study treatment actually received by each subject.

Pharmacokinetic Analysis Set

The PK analysis set will consist of all subjects who were correctly administered at least 1 ME3183 dose and where ME3183 or CCI [REDACTED] concentration data is available without any protocol deviation interfering with these results. Analyses in the PK analysis set will be based on the study treatment actually received by each subject.

CCI [REDACTED]

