### 10.1. Primary Efficacy Endpoint and Analysis

The primary efficacy endpoint is the proportion of subjects achieving  $\geq 75\%$  reduction from baseline in the PASI score at Week 16. Baseline is defined as the PASI score on Day 1 pre-dose.

For each ME3183 treatment group, the difference in the proportion of subjects achieving the difference in PASI-75 (ME3183 – placebo) and its 95% confidence interval (CI) will be estimated and tested for superior treatment effect using the Cochran-Mantel-Haenszel (CMH) test with prior receipt of any biologics for psoriasis (bio-naïve vs non-bio-naïve) as adjustment factor at a 1-sided significance level of  $\alpha = 0.025$ .

Analysis will be conducted using observed data at Week 16 only (complete-case analysis). In the presence of missing data, additional sensitivity analysis will be conducted using both LOCF and NRI. Under LOCF, the last non-missing PASI score will be carried forward to Week 16, based on which the subject will be considered as responder or non-responder and summarized accordingly. Under NRI, subjects with missing PASI scores at Week 16 will be considered non-responders.

Subgroup analysis will be carried out stratified by the prior receipt of any biologics for psoriasis (bio-naïve vs non-bio-naïve), where Fisher's exact test will be used instead of CMH for superiority.

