## 18. Index of Tables

Table Number	Name	Analysis Set
14.1.1.1	Number of Subjects Enrolled and Study Termination	(Screened/Randomized Set)
14.1.2.1	Major Protocol Deviations	(Randomized Set)
14.1.2.2	Reasons for Exclusions from Analysis Sets	(Randomized Set)
14.1.3.1.1	Subject Demographic and Baseline Characteristics	(Randomized Set)
14.1.3.1.2	Subject Demographic and Baseline Characteristics	(Safety Analysis Set)
14.1.3.1.3	Subject Demographic and Baseline Characteristics	(Full Analysis Set)
14.1.3.1.4	Subject Demographic and Baseline Characteristics	(Per Protocol Set)
14.1.3.2.1	Baseline Disease Characteristics	(Randomized Set)
14.1.3.2.2	Baseline Disease Characteristics	(Safety Analysis Set)
14.1.3.2.3	Baseline Disease Characteristics	(Full Analysis Set)
14.1.3.2.4	Baseline Disease Characteristics	(Per Protocol Set)
14.1.3.3	Medical History	(Safety Analysis Set)
14.1.4.1.1	Prior Medications	(Safety Analysis Set)
14.1.4.1.2	Concomitant Medications	(Safety Analysis Set)
14.1.4.2.1	Prior Medical/Surgical Procedures	(Safety Analysis Set)
14.1.4.2.2	Concomitant Medical/Surgical Procedures	(Safety Analysis Set)
14.1.4.3	Prior Biologics or Systemic Treatment for Psoriasis	(Safety Analysis Set)
14.1.5	Extent of Exposure	(Safety Analysis Set)
14.1.6	Treatment Compliance	(Safety Analysis Set)
14.2.1.1.1.1	Proportion of Subjects Achieving PASI-75 at Week 16, Complete Case Analysis	(Full Analysis Set)
14.2.1.1.1.2	Proportion of Subjects Achieving PASI-75 at Week 16 Stratified by Receipt of Any Biologics for Psoriasis, Complete Case Analysis	(Full Analysis Set)
14.2.1.1.2.1	Proportion of Subjects Achieving PASI-75 at Week 16, LOCF	(Full Analysis Set)
14.2.1.1.2.2	Proportion of Subjects Achieving PASI-75 at Week 16 Stratified by Receipt of Any Biologics for Psoriasis, LOCF	(Full Analysis Set)
14.2.1.1.3.1	Proportion of Subjects Achieving PASI-75 at Week 16, NRI	(Full Analysis Set)
14.2.1.1.3.2	Proportion of Subjects Achieving PASI-75 at Week 16 Stratified by Receipt of Any Biologics for Psoriasis, NRI	(Full Analysis Set)
14.2.1.2.1.1	Proportion of Subjects Achieving PASI-75 at Week 16, Complete Case Analysis	(Per Protocol Set)
14.2.1.2.1.2	Proportion of Subjects Achieving PASI-75 at Week 16 Stratified by Receipt of Any Biologics for Psoriasis	(Per Protocol Set)
14.2.1.2.2.1	Proportion of Subjects Achieving PASI-75 at Week 16, LOCF	(Per Protocol Set)

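### Treated subjects with no post-baseline PASI are outside the FAS, so the non-responder (NRI) sensitivity analyses leave them out instead of counting them as failures

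*SAP*

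**What the plan says.** SAP 6.4 sets three conditions for the FAS: randomised, dosed at least once, and "have at least 1 evaluable post-baseline time point for primary endpoint will be included in the full analysis set (FAS"). Protocol 15.2 has the same condition: "have at least 1 evaluable post-Baseline time point for primary endpoint will be included in the full analysis set (FAS"). SAP 6.4 adds: "The FAS will be used for all analyses of efficacy endpoints".

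For PASI-75 at Week 16, SAP 10.1 states the main approach as "Analysis will be conducted using observed data at Week 16 only (complete-case analysis"), with LOCF and NRI as sensitivity analyses. Its NRI rule is: "Under NRI, subjects with missing PASI scores at Week 16 will be considered non-responders". SAP 10.2 extends NRI to the PASI responder endpoints at every visit and to the sPGA responder endpoint.

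The SAP 18 table index lists "Proportion of Subjects Achieving PASI-75 at Week 16, NRI" for the FAS and again for the PPS, which SAP 6.5 defines as a subset of the FAS. The NRI tables for the secondary PASI and sPGA endpoints are likewise on the FAS or PPS. None uses a wider set.

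On timing, the protocol synopsis says efficacy "will be assessed at Baseline (Day 1) and at Weeks 1, 2, 4, 8, 12, 16, and 20", so the first scheduled post-baseline PASI is at Week 1 (Day 8, plus or minus 1 day, in Table 1). For subjects who stop early, protocol 7.4 says "all data collected at Visit 8 (Day 113) should be collected at the time of early termination", and asks for a further return 4 weeks after the last dose. Table 1 includes PASI at both of those visits.

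**The concern.** NRI classifies a subject from one fact, the absence of a Week 16 score, and needs no earlier score. The FAS condition is sensible for LOCF and for the repeated-measures models, which have nothing to work with otherwise. Applied to NRI it defeats the purpose. A subject who takes drug, stops in the first days and is never scored again disappears from numerator and denominator. A subject who stops just after the Week 1 visit counts as a failure.

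FAS membership then depends on something that happens after randomisation and that treatment may influence. Protocol 5.3 expects nausea, vomiting and diarrhoea as class effects, protocol 5.2.2 reports them with repeated dosing in healthy subjects, and steady state came at about Day 3 to 4, before the first post-baseline visit. If early exits are commoner on active, the affected NRI comparisons tilt towards the drug, in the analysis meant to be strict about drop-out.

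**Working it through.** The plan states no power, effect size or response rate (SAP 4.3: no formal sample size calculation), so there is no figure of its own to reproduce on this point. What follows is an illustration with assumed counts.

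**Inputs from the documents**
- 25 subjects per arm (SAP 4.3).
- Drop-out 10%, that is 0.10 × 25 = 2.5 per arm; timing not given (SAP 4.3).
- One-sided level 0.025, CMH test (SAP 10.1).

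**Assumed**
- r responders in an active arm, range 5 to 13.
- k treated subjects in that arm with no post-baseline PASI, 1 or 2. If the whole 10% left before any PASI, k would be 2 to 3, so two is already towards the upper end.
- All 25 randomised subjects in each arm took at least one dose.

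**Step 1: who is affected.** To have no post-baseline PASI at all, a treated subject must miss Visit 3 and the early-termination visit. The follow-up visit must be missed too if a PASI at that visit counts as evaluable, which the text leaves open.

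**Step 2: effect on one arm's NRI rate.** NRI on all treated subjects gives r/25. NRI on the FAS gives r/(25 − k). The overstatement is the difference.

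| r | r/25 | k = 1 | rise | k = 2 | rise |
|---|---|---|---|---|---|
| 5 | 20.0% | 5/24 = 20.8% | 0.8 | 5/23 = 21.7% | 1.7 |
| 8 | 32.0% | 8/24 = 33.3% | 1.3 | 8/23 = 34.8% | 2.8 |
| 10 | 40.0% | 10/24 = 41.7% | 1.7 | 10/23 = 43.5% | 3.5 |
| 13 | 52.0% | 13/24 = 54.2% | 2.2 | 13/23 = 56.5% | 4.5 |

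With k = 0 nothing changes.

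**Step 3: effect on the comparison.** Mantel-Haenszel test, taken as a single stratum without continuity correction. With a of n responders on active, b of m on placebo, N = n + m and t = a + b:

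E = nt/N, V = nmt(N − t)/[N²(N − 1)], z = (a − E)/√V.

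- 7/25 v 2/25: E = 4.500, V = 1.883, z = 1.822, p = 0.034.
- 7/24 v 2/25: E = 4.408, V = 1.874, z = 1.893, p = 0.029.
- 7/23 v 2/25: E = 4.3125, V = 1.864, z = 1.969, p = 0.0245.
- 7/23 v 2/24: E = 4.404, V = 1.858, z = 1.904, p = 0.028.
- 7/23 v 2/23: E = 4.500, V = 1.850, z = 1.838, p = 0.033.

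Two exclusions on active and none on placebo take this example across 0.025 with no added response. One placebo exclusion alongside them, or two, leaves it above.

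**Step 4: how special the example is.** For placebo counts 0 to 7, starting from 25 per arm, a single exclusion on active crosses 0.025 only at 10 v 4 (p = 0.031 to 0.0245). Two exclusions on active cross it at 7 v 2, 10 v 4, 11 v 5, 12 v 6 and 13 v 7.

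**The case against.** The case for leaving the plan alone has real weight.

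- **The main result cannot change.** A reader might infer from the 0.025 crossing that the trial's primary conclusion is at risk. It is not: complete-case analysis drops everyone without a Week 16 score whatever the FAS rule says, and no decision rule in the documents rests on NRI. This stands.
- **Few subjects may qualify.** Stopping drug early is not enough, because PASI is also due at early termination and at follow-up. This narrows the group but does not empty it, since subjects may return for neither.
- **The direction is not shown.** It is tempting to say that the bias favours the drug. The documents give no rate of stopping before Day 8 and no dose relation for it. In the multiple-dose Phase 1 study most events were mild and all resolved during dosing. Only 'could favour' is supported.
- **Exclusions are visible.** SAP 9.1 and Table 14.1.2.2 report numbers and reasons by arm, so a reader could restore excluded subjects as failures. That helps, but the planned NRI tables would still be wrong by their own definition.
- **A stricter reading of the wording.** The primary endpoint exists only at Week 16, so one might infer that the FAS means Week 16 completers, leaving LOCF and NRI nothing to impute. The phrase 'at least 1' presupposes several time points, and LOCF and NRI tables are planned on the FAS, so the context rules this out. It is a wording point only.

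**Conclusion.** The point holds for the NRI analyses: the sensitivity analysis of the primary endpoint and the NRI analyses of the secondary PASI and sPGA responder endpoints. On the plan's own text, a treated subject with no post-baseline PASI is never counted as a non-responder, contrary to the stated NRI rule.

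The effect on an arm's rate is 0.8 to 2.2 points for one exclusion and 1.7 to 4.5 for two, and zero if there are none. A one-sided p-value moves materially only if exclusions are unbalanced towards active and the result lies near the threshold. These sizes rest on assumed responder and exclusion counts and on a single-stratum test; the plan's test adjusts for prior biologic use. The correction is worth making because it is cheap and removes a possible bias from the one analysis intended to penalise drop-out. It does not put the main analysis in doubt.

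**What to change.** - In SAP 6.4, 10.1 and 10.2, run the NRI analyses of PASI and sPGA response on all randomised subjects who took at least one dose, by randomised group, counting those with no post-baseline score as non-responders.
- Define that set explicitly. The safety analysis set has the same entry condition but groups subjects by treatment received (SAP 6.3), so it cannot simply be reused.
- Keep the present FAS for the LOCF, MMRM and observed-data analyses.
- Replace 'time point for primary endpoint' with 'post-baseline PASI assessment', and say whether a Week 20 PASI qualifies.
- Record the departure from protocol 15.2 and 15.3 in SAP 14, which now states that there are no changes.
- While editing, correct SAP 7.1, which points to Sections 6.2 and 6.3 for the FAS and PPS; those sections now define the randomised and safety sets.

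The cost is one more analysis set, a changed denominator in the NRI tables, and NRI response rates that may be slightly lower. No new data are needed.
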